### Model Results Presentation

- The estimated treatment ratios together with 95% CIs (back-transformed from the differences on the log-scale) will be produced for each treatment group along with the treatment comparisons and p-values.
- In addition the percentage change from baseline will also be presented where this is calculated as:  

$$\% \text{ change from baseline} = (\text{ratio}-1)*100$$

The following endpoints will be summarised descriptively only. No analysis will be performed and all data will be reported as collected excluding data after which participants had reached loss of asthma control/withdrawn early from study treatment and restarted their standard of care medication (Primary Estimand only), using the modified Intent to Treat population:

- Change from baseline in ACQ-5 absolute score at each week from Week 1 to Week 16.
- Participants with  $\geq 0.5$  point ACQ-5 score decrease from baseline (responder) at each week from Week 1 to Week 16.
- Change from baseline in SGRQ total score at Weeks 4, 8, 12 and 16.
- St. George's Respiratory Questionnaire (SGRQ) responders (at least a 4 unit improvement from baseline) at Weeks 4, 8, 12 and 16.
- Change from baseline in mean morning peak expiratory flow (PEF) and mean evening PEF over each four weeks of the 16 week treatment period. Note: Each PEF is taken in triplicate with the maximum value being used.
- Change from baseline in mean daytime asthma symptom score over each four weeks of the 16 week treatment period.
- Changes from baseline in night-time awakenings due to asthma symptoms requiring rescue medication use over each four weeks of the 16 week treatment period. Note: This is the change from baseline in the average number of nights a participant woke up at least once and had to use their rescue medication.
- Change from baseline in rescue medication use (albuterol/salbutamol): mean number of inhalations per day over each four weeks of the 16 week treatment period.

## **8. SAFETY ANALYSES**

The safety analyses will be based on the Safety including GCP non-compliant subjects population, unless otherwise specified. The details of the planned displays are provided in [Appendix 10: List of Data Displays](#).

### **8.1. Adverse Events Analyses**

Adverse events analyses including the analysis of adverse events (AEs), Serious (SAEs) and Adverse Events of Special Interest (AESIs) will be based on GSK Core Data Standards.

### **8.2. Adverse Events of Special Interest Analyses**

A comprehensive list of MedDRA terms based on clinical review will be used to identify each type of event. Changes to the MedDRA dictionary may occur between the start of the study and the time of reporting and/or emerging data from on-going studies may highlight additional adverse events of special interest, therefore the list of terms to be used for each event of interest and the specific events of interest will be based on the safety review team (SRT) agreements in place at the time of reporting.

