### **3. PLANNED ANALYSES**

#### **3.1. End of Treatment Phase Analyses**

The End of Treatment Phase Analysis will be performed after the completion of the following sequential steps:

1. All subjects have completed the Week 16 visit or the Early Withdrawal visit
2. All required database cleaning activities have been completed and database release has been declared by Data Management.
3. All criteria for unblinding the randomisation codes have been met.
4. Randomisation codes have been distributed according to RandAll NG procedures.

Due to an inability to lock log forms used for collection of exacerbation data, the end of treatment phase analysis will be considered an interim analysis for both efficacy and safety. Any safety data collected for participants who have completed clinic visits after Week 16 will also be cleaned and included in the analysis.

All participants will have completed the active treatment phase of the study by the time of the interim, so no modifications will be made to the study as a result of the End of Treatment Phase Analysis. The Final Analysis is intended to be an analysis of safety data collected in the Post-treatment Follow-Up phase.

The sponsor will be unblinded to the results of the analysis.

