#### **3.2. Final Analyses**

The final planned primary analyses will be performed after the completion of the following sequential steps:

- All subjects have completed the study.
- All required database cleaning activities for data after Week 16/ Early Withdrawal as well as data collected on log pages have been completed.
- Final database release and database freeze has been declared by Data Management.

No unblinding will take place as part of the final analysis as all participants will have already been unblinded during the End of Treatment Phase Analysis.

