#### 4.1. Protocol Deviations

All important protocol deviations (including deviations related to study inclusion/exclusion criteria, conduct of the trial, patient management or patient assessment) will be summarised and listed.

Protocol deviations will be tracked by the study team throughout the conduct of the study in accordance with the Protocol Deviation Management Plan [21-Aug-2017 (Version 1) or later].

- Data will be reviewed prior to unblinding and freezing the database to ensure all important deviations are captured and categorised on the protocol deviations dataset.
- This dataset will be the basis for the summaries and listings of protocol deviations.

A separate summary and listing of all inclusion/exclusion criteria deviations will also be provided. This summary will be based on data as recorded on the inclusion/exclusion page of the eCRF.

Note: Inclusion and exclusion criteria deviations are always reported as important.

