### 12.4.2. Treatment Emergent Flag for Adverse Events

Flag	Definition
Treatment Emergent	
If AE onset date is on or after treatment start date & on or before treatment stop date + 28 days.
 
Study Treatment Start Date ≤ AE Start Date ≤ Study Treatment Stop Date + 28 days

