## 12.6.4. Safety

Adverse Events
Adverse Events of Special Interest (AESI)

Systemic Allergic/Hypersensitivity and Non-allergic Reactions:
 
 
• Hypersensitivity (SMQ) [narrow]
 
• Anaphylactic reaction (SMQ) [narrow]
 
• Angioedema (SMQ) [narrow]
 
 
Alterations in immune response (infections)
 
All infections and serious infections reported under the MedDRA system organ class of 'Infections and Infestations'. Specific events of interest are opportunistic infections with preferred terms matching identified/pre-determined terms based on a published list of pathogens and/or presentations of specific pathogens to be considered as opportunistic infections in the setting of biologic therapy [Winthrop, 2015].
 
Alterations in immune response (malignancies):
 
All neoplasms reported under the MedDRA system organ class of 'Neoplasms, benign, malignant and unspecified (including cysts and polyps)'. Specific events of interest are malignancies which will be identified through matching of collected preferred terms with those from the following:
 
Sub-SMQs under the Malignancies SMQ:
 
 
• Malignant tumours sub-SMQ (narrow terms)
 
• Tumours of unspecified malignancy sub-SMQ (narrow terms)
 
 
Alterations in cardiovascular safety:
 
Cardiac disorders and serious cardiac disorders reported under the MedDRA system organ class of 'Cardiac Disorders'. Serious cardiac, vascular and thromboembolic (CVT) events, identified as all serious events classified under the MedDRA system organ classes of 'Cardiac Disorders' and of 'Vascular Disorders', and thromboembolic events identified through matching of collected preferred terms with those from the following:
 
Sub-SMQs under the Embolic and thrombotic events SMQ:
 
 
• Embolic and thrombotic events, arterial sub-SMQ (narrow terms)
 
• Embolic and thrombotic events, venous sub-SMQ (narrow terms)
 
• Embolic and thrombotic events, vessel type unspecified and mixed arterial and venous sub-SMQ (narrow terms)
 
 
Sub-SMQs under the Ischaemic Heart Disease SMQ
 
 
• Myocardial infarction sub-SMQ (narrow terms)
 
• Other Ischaemic heart disease sub-SMQ (narrow terms)
 
 
Sub-SMQs under the Central Nervous System Vascular Disorders SMQ
 
 
• Ischaemic central nervous system vascular conditions sub-SMQ (narrow terms)
 
• Central nervous system vascular disorders, not specified as haemorrhagic or ischaemic sub-SMQ (narrow terms)
 
• Serious ischemic adverse events, a subset of the serious CVT events identified through matching of collected preferred terms with those from the following:
 
 
Local Injection Site Reactions
 
Local injection site reactions are identifying through preferred terms which had been selected by medical review of the MedDRA dictionary and are provided in a separate spreadsheet.

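### Section 8.2 lets the AESI terms and categories set out in 12.6.4 be replaced by safety review team agreements current at reporting, which for the final report is after unblinding, with no duty to label a departure

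*SAP*

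**What the plan says.** Section 8.2 says that a term list from clinical review will identify each type of AESI. Because MedDRA may change and other studies may bring new risks to light, it adds that the term lists and "the specific events of interest will be based on the safety review team (SRT) agreements in place at the time of reporting". Both the coding of each category and the set of categories are therefore open.

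Section 12.6.4 gives a baseline. Hypersensitivity uses three narrow standardised queries. Infections use a system organ class, with a cited published list for opportunistic infections. Malignancies and cardiovascular events use system organ classes plus named sub-queries. Local injection site reactions rest on "preferred terms which had been selected by medical review of the MedDRA dictionary and are provided in a separate spreadsheet", for which no version or date is given.

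On timing, the fourth and last step listed in Section 3.1 before the ETP analysis is "Randomisation codes have been distributed according to RandAll NG procedures". The same section says "The sponsor will be unblinded to the results of the analysis", and Section 3.2 says that by the final analysis "all participants will have already been unblinded during the End of Treatment Phase Analysis". Section 12.10.7 schedules AESI Tables 3.16 to 3.19 for both the ETP report and the final (SAC) report.

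**The concern.** An AESI table by arm is read as a comparison on risks named in advance. Under the rule in 8.2, the final version may instead reflect categories or terms chosen when the people choosing them could see which arm had the events. The SAP does not require such a change to be marked, so terms settled before and after unblinding could sit in one table without distinction. At stake is whether Tables 3.16 to 3.19 in the final report can be read as prespecified.

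**Working it through.** The SAP has no figure of its own to reproduce here. The check is one of sequence and coverage, with some simple counts.

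**1. Order of events.** From 3.1 and 3.2: codes distributed (step 4), then the ETP analysis with the sponsor unblinded, then follow-up, then the final analysis with no blind left. Planned follow-up runs from Week 16 to Week 28: 28 − 16 = 12 weeks, or 12 × 7 = 84 days. The time of reporting for the final report is therefore after unblinding.

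**2. Is the list fixed anywhere before step 4?** None of the four steps in 3.1 names it. Step 3 refers to criteria for unblinding without listing them. The pre-unblinding review of classifications that the SAP does spell out, in 4.1, is for protocol deviations: "Data will be reviewed prior to unblinding and freezing the database to ensure all important deviations are captured". Section 3.1 also promises that "no modifications will be made to the study as a result of the End of Treatment Phase Analysis", but that concerns the conduct of the study. It does not hold the AESI list still when 8.2 expressly allows it to move. No MedDRA version is named.

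**3. Outputs exposed.** 4 tables × 2 reports = 8 deliveries, of which the 4 at SAC follow unblinding.

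**4. Would the on-treatment tables still be open?** Treatment-emergent events are those with onset "on or before treatment stop date + 28 days". The planned last dose is on Day 85 (Week 12), so the window closes on Day 85 + 28 = 113. The planned Week 16 day is 16 × 7 + 1 = 113. Apart from visit-window slippage and late data cleaning, the events behind Tables 3.16 and 3.17 have all occurred by the ETP analysis. A change in those two tables between reports could then come largely from a change in definitions.

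**5. How much is anchored?** Of the five categories in 12.6.4, four are anchored by system organ class or standardised query (5 − 1 = 4). A departure in any of those would show against the SAP. Only injection-site reactions have no definition in the SAP text.

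**6. Scale of one reclassification.** One participant moves an arm's rate by 100/n percentage points. At the 70 evaluable per arm of Section 2.6 this is 100/70 = 1.4. At an assumed 90 per arm, since the safety population also includes participants excluded for GCP failures, it is 100/90 = 1.1. These figures show the granularity of the tables and are not an estimated effect. The SAP gives no expected number of reclassified events.

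**The case against.** The best case for the plan is that 8.2 is a sensible safety rule. Its two stated reasons, dictionary changes and emerging data from ongoing studies, are legitimate, and neither refers to arm-level results from this trial. A plan that could not show a newly recognised risk would be worse. The tables are descriptive. Whatever is flagged as an AESI, all events remain in the general adverse event and serious adverse event tables (3.2, 3.3, 3.11, 3.12). Listings 21 and 55, due at both reports, should make a change traceable. The spreadsheet wording describes a selection already made. Section 12.5.1 plans a blinded dry run, so some reporting work is done before unblinding. The safety review team agreements, the unblinding criteria and the separate internal safety review committee documents are not to hand, and any of them may carry a dated list.

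Most of this stands, and it limits the point to a minor one. It does not remove it. The dry run is not said to freeze the AESI list. Listings make a change discoverable but do not label it. Even if the agreements do predate code release, 8.2 does not require that they should. The legitimate reasons for change can be met by showing additions separately.

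A reader might infer that the plan contains no AESI definitions before the codes are released. Section 12.6.4 contradicts that. A reader might also infer that definitions were, or will be, altered in the light of results. Nothing in the document shows this; the rule only permits it.

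**Conclusion.** The point holds as a minor, inexpensive improvement. The SAP has baseline AESI definitions but also a rule that lets them be replaced, in terms and in categories, after the sponsor knows treatment allocation, with no obligation to mark the change. The effect is confined to how far the descriptive AESI summaries in the final report can be taken as prespecified. No event is lost, and no test, primary analysis or general adverse event table is affected.

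The conclusion rests on reading the time of reporting, for the SAC deliveries, as the time of the final report, and on the order of steps in 3.1 and 3.2. It does not assume that any agreement is in fact dated after unblinding.

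The serious-ischaemic line in 12.6.4 introduces a list of terms but none follows. That is a separate editorial matter and does not bear on timing.

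**What to change.** In 8.2, replace the reference to the time of reporting. For Tables 3.16 to 3.19 at both ETP and SAC, use the 12.6.4 definitions together with the safety review team list and the injection-site spreadsheet in place before step 4 of 3.1, each cited by version, date and MedDRA version. After that point, allow only mechanical mapping between MedDRA versions. Put any AESI or term added later in a separate display, labelled as added after unblinding and with the reason given, so that new signals are still reported.

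The cost is a change of SAP wording, a dated list, and one extra display if anything is added. No new data are needed, because AESI flags are derived from adverse events already coded.

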### **8.3. Vital Signs, Electrocardiogram (ECG) and Holter**

Summary statistics for vital signs at baseline, weeks 1, 2, 4, 6, 8, 10, 12, 14, 16, 20, 24 and 28 will be produced along with change from baseline summaries for each post baseline timepoint. In addition, the change between post-dose and pre-dose vital signs measurements will be summarised at weeks 0, 4, 8 and 12.

Similar 12-lead electrocardiogram (ECG) measurements at baseline, weeks 4, 8, 12 and 16 will be produced along with change from baseline summaries for each post baseline timepoint, and changes between post-dose and pre-dose in 12-lead ECG measurements at weeks 0, 4, 8 and 12.

24 hour Holter measurements collected at baseline, weeks 0, 4 and 12 will be summarised along with change from baseline at weeks 0, 4 and 12. Only participants with at least 16hrs worth of data will be included in any tables however all data will be listed.

### **8.4. Clinical Chemistry, Haematology and Cardiac Markers**

Summaries of clinical chemistry results at baseline, weeks 2, 4, 8, 12, 16 and 28 along with change from baseline for all post-baseline measurements will be produced.

Similarly, haematology and cardiac markers at baseline, weeks 1, 2, 4, 6, 8, 10, 12, 14, 16 and 28 along with change from baseline for all post-baseline measurements will also be produced.

## **8.5. Antibodies**

Summaries of the incidence of and titres of anti- GSK3772847 antibodies at weeks 0\*, 2, 4\*, 8\*, 12\*, 16, 20, 24 and 28.

\* = Pre-dose only

## **8.6. Clinical Laboratory Analyses**

Laboratory evaluations including the analyses of liver function tests will be based on GSK Core Data Standards.

## **9. PHARMACOKINETIC ANALYSES**

Due to the time required to analyse PK samples, no PK outputs will be included in the end of treatment phases analysis.

### **9.1. Secondary Pharmacokinetic Analyses**

#### **9.1.1. Endpoint / Variables**

Serum concentrations of GSK3772847 by nominal time.

#### **9.1.2. Population of Interest**

The secondary pharmacokinetic analyses will be based on the Pharmacokinetic population, unless otherwise specified.

#### **9.1.3. Strategy for Intercurrent (Post-Randomisation) Events**

Not applicable.

#### **9.1.4. Statistical Analyses / Methods**

- No statistical analysis will be performed.
- Serum concentration will be summarised descriptively with summary figures being produced.
- Scatter plots of trough serum concentration vs FeNO, trough serum concentration vs blood eosinophils, and trough serum concentration vs IgE at Week 4 only will also be produced.

## 10. PHARMACODYNAMIC AND BIOMARKER ANALYSES

### 10.1. Secondary Pharmacodynamic Analyses

#### 10.1.1. Endpoint / Variables

Free and total soluble ST2 levels in serum

#### 10.1.2. Summary Measure

Free soluble ST2: Summary statistics and percentage change from baseline

Total soluble ST2: Summary statistics and percentage change from baseline

Only pre-dose trough sST2 will be used for analysis. Post-dose trough sST2 will be summarised only.

#### 10.1.3. Population of Interest

The secondary pharmacodynamics analyses will be based on the modified Intent to Treat population, unless otherwise specified.

#### 10.1.4. Strategy for Intercurrent (Post-Randomisation) Events

Not applicable.

#### 10.1.5. Statistical Analyses / Methods

Endpoint / Variables

 
Percentage change from baseline in free sST2 (On-treatment)
 
Percentage change from baseline in free sST2 (Post-treatment)
 
Percentage change from baseline in total sST2 (On-treatment)
 
Percentage change from baseline in total sST2 (Post-treatment)
 

Strategy for Intercurrent (Post-Randomisation) Events
No intercurrent events are considered for this endpoint. All data will be used as collected.
Model Specification

 
The ratio of post-baseline sST2 values to baseline sST2 values will be log transformed prior to analysis. Note: <math>\text{Log}(\text{post baseline sST2} / \text{baseline sST2})</math> is equivalent to <math>\text{log}(\text{post baseline sST2}) - \text{log}(\text{baseline sST2})</math>.
 
A repeated measures model with terms for treatment, visit, visit by treatment, the logarithm of baseline sST2, the logarithm of baseline sST2 by visit and screening eosinophil strata will be fitted.
 
 
Model Structure:
 
 
The variance-covariance matrix will be assumed unstructured.
 
Kenward Roger (KR) method will be used for calculating degrees of freedom. If the analysis does not run using the KR method then the residual method will be used instead.
 

 
An observed margins (OM) dataset will be used to derive the LS means using coefficients which are based on the subjects used in the analysis. This is a dataset with a row for every subject-visit combination that contains all of the covariates. The OM will be at the average baseline of free sST2 (either On-treatment or Post-treatment according to the model).
 

Model Checking & Diagnostics

 
Distributional assumptions underlying the model used for analysis will be examined by obtaining a normal probability plot of the residuals and a plot of the residuals versus the fitted values (i.e. checking the normality assumption and constant variance assumption of the model respectively) to gain confidence that the model assumptions are reasonable.
 

Model Results Presentation


 
The estimated treatment ratios together with 95% CIs (back-transformed from the differences on the log-scale).
 

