
Only data until Week 4 (down titration of ICS) will be analysed, all data post Week 4 will be summarised descriptively only. Both FeNO and eosinophils have the ratio of post-baseline values to baseline values log transformed prior to analysis. For FeNO where multiple measurements can be taken at a visit, the data will be log transformed (using the natural logarithm (ln) hereby referred to as log) and the average log transformed value used as the visit value.
 
FeNO Analysis Model: A repeated measures model with terms for log(baseline FeNO), treatment, visit, screening eosinophil strata and interaction terms for log(baseline FeNO) by visit, treatment by visit and screening eosinophil strata by visit.
 
Eosinophil Analysis Model: A repeated measures model with terms log(baseline eosinophils), treatment, visit and interaction terms for log(baseline eosinophils) by visit and treatment by visit.
 
Model Structure:
 
 
The variance-covariance matrix will be assumed unstructured.
 
Kenward Roger (KR) method will be used for calculating degrees of freedom. If the analysis does not run using the KR method then the residual method will be used instead.
 
An observed margins (OM) dataset will be used to derive the LS means using coefficients which are based on the subjects used in the analysis. This is a dataset with a row for every subject-visit combination that contains all of the covariates. The OM will be at the average logarithm of baseline FeNO or average logarithm of baseline eosinophils dependent on the model.
 
 
Due to a large amount of FeNO data being outside the normal range, further analysis of FeNO may be explored.

Model Checking & Diagnostics

 
Distributional assumptions underlying the model used for analysis will be examined by obtaining a normal probability plot of the residuals and a plot of the residuals versus the fitted values (i.e. checking the normality assumption and constant variance assumption of the model
 

respectively) to gain confidence that the model assumptions are reasonable.

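### The LS means of all four sST2 models are set at the average baseline of free sST2: not the log scale of the covariate in any model, and the wrong analyte in the two total sST2 models

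*SAP*

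**What the plan says.** SAP Section 10.1.5 lists four endpoints under one model specification. Two are for free sST2; the others are "Percentage change from baseline in total sST2 (On-treatment") and "Percentage change from baseline in total sST2 (Post-treatment"). The response is on the log scale: "The ratio of post-baseline sST2 values to baseline sST2 values will be log transformed prior to analysis". The baseline enters on the log scale too, with a visit interaction: "the logarithm of baseline sST2, the logarithm of baseline sST2 by visit and screening eosinophil strata will be fitted". There is no baseline-by-treatment term.

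On the LS means, the section first describes the observed margins (OM) dataset, built from the analysed subjects: "This is a dataset with a row for every subject-visit combination that contains all of the covariates". It then fixes the reference value for all four models: "The OM will be at the average baseline of free sST2 (either On-treatment or Post-treatment according to the model").

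For the same kind of log-ratio model, the FeNO and eosinophil block of Section 7.2.4.1 says: "The OM will be at the average logarithm of baseline FeNO or average logarithm of baseline eosinophils dependent on the model".

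**The concern.** The reference value departs from the model it belongs to in two ways. In all four models the covariate is a logarithm, but the stated reference is an average that is not logged. In the two total sST2 models the reference is also taken from a different analyte, which is not in the model. The parenthesis lets the value vary by study phase but not by analyte.

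The model has no interaction of treatment with baseline or with stratum, so the reference value cannot affect a between-arm comparison. It affects only the arm-level LS means and whatever is back-transformed from them. The endpoints are named as percentage change from baseline, and Tables 6.2, 6.4, 6.6 and 6.8 are titled as analyses of that quantity. Any arm-level, model-based percentage change shown there would describe a participant with an unintended baseline.

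**Working it through.** **How the plan words this elsewhere (SAP Sections 7.2.4.1 and 10.1.5).**

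| Model | Baseline covariate | Stated reference for LS means | Match |
|---|---|---|---|
| FEV1 | unlogged | average baseline, unlogged | yes |
| FeNO, eosinophils | log, own analyte | average log baseline, own analyte | yes |
| Free sST2 (two models) | log free | average baseline of free sST2, no log | wrong scale |
| Total sST2 (two models) | log total | average baseline of free sST2, no log | wrong scale and analyte |

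The plan keeps logged and unlogged averages apart in the other blocks, so the sST2 wording is hard to read as house shorthand.

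**Effect on the estimates.** The SAP states no figure on this point, so there is nothing to reproduce. Write b for the slope of the log ratio on log baseline at a visit, x* for the reference used and x̄ for the mean log baseline of the modelled analyte. The arm-level LS mean moves by b(x* − x̄), so the back-transformed post/baseline ratio is multiplied by exp(b(x* − x̄)). The factor is the same in both arms and cancels from the treatment ratio.

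**Assumed inputs (none are in the SAP):** b from −0.2 to −0.8; SD of log baseline (s) from 0.3 to 0.8 with a log-normal baseline; average free divided by geometric mean total (r) from 0.5 to 1.25.

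- (a) *The average is logged before use, right analyte.* Factor exp(b·s²/2). At s = 0.3, b = −0.2: exp(−0.009) = 0.991. At s = 0.5, b = −0.5: exp(−0.0625) = 0.939. At s = 0.8, b = −0.8: exp(−0.256) = 0.774.
- (b) *Total model set at the log of the free average.* Factor r^b. At r = 0.5: 1.149 (b = −0.2), 1.414 (b = −0.5), 1.741 (b = −0.8). At r = 1: 1.000. At r = 1.25, b = −0.8: 0.837.
- (c) *Unlogged mean m entered as the value of the log covariate,* taking x̄ = ln m. Factor exp(b(m − ln m)). At m = 1.5, b = −0.2: 0.803. At m = 5, b = −0.5: 0.184. At m = 20, b = −0.5: 0.0002.

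**Simulated fit.** 70 per arm, three visits and the fixed effects of Section 10.1.5, with a random intercept in place of the unstructured covariance. Assumed geometric mean baseline 20, log SD 0.5, slope about −0.5. First visit:

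| Reference | Placebo % change | GSK3772847 % change | Ratio |
|---|---|---|---|
| Mean log baseline | +0.8 | −54.7 | 0.4499 |
| Log of arithmetic mean | −4.1 | −56.8 | 0.4499 |
| Log of half the arithmetic mean | +36.3 | −38.7 | 0.4499 |
| Raw mean | about −100 | about −100 | 0.4499 |

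In the third row both arms move by the same factor: 1.363/1.008 = 1.352 for placebo and 0.613/0.453 = 1.353 for GSK3772847. At the other two visits the ratios (0.3707 and 0.3384) were likewise identical under all four references.

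**The case against.** A reader might infer that the reported target-engagement results will be wrong. The SAP does not support that, for four reasons.

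- **Specified output.** The results presentation for sST2 names only treatment ratios with 95% confidence intervals, and these cannot move. The FeNO and eosinophil block does call for per-arm ratios and percentage change; the sST2 block has no such line. That arm-level model output will appear is inferred from the endpoint names and table titles. This stands, and it makes the consequence conditional.
- **Descriptive tables.** Tables 6.1, 6.3, 6.5 and 6.7 summarise raw values and percentage change by arm without any model, so arm-level target engagement can be read there. This stands.
- **Default behaviour.** An OM dataset built as the preceding sentence describes would give the mean of the modelled log covariate by itself. The error arises only if someone programs the stated value. For a total sST2 model, that means importing the mean of a variable that is not in it. The sentence may be loose drafting. This stands against calling the results wrong, but it leaves two adjacent sentences pointing to different values, and programmer and QC could each follow a different one.
- **Size.** Every input is assumed, and the large shifts come from extreme combinations. Scenario (c) gives results so implausible that QC should notice. In scenario (a) the LS mean is still a valid adjusted mean, at a baseline other than the intended one. This stands too.

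None of this makes the sentence correct. Arm-level LS means are the only thing it governs, and taken literally it misplaces them.

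**Conclusion.** The sentence is wrong as written, and the point is minor. It gives the wrong scale for all four models and the wrong analyte for two, and it fits neither the OM-dataset sentence before it nor the FeNO and eosinophil rule. Harm requires three things: the value is programmed literally, the baseline slope is not zero, and arm-level LS means or percentage changes are displayed.

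The size cannot be computed from the SAP. Under the assumed ranges, the arm-level ratio is multiplied by 0.99 to 0.77 through the scale alone, if the average is logged before use. It is multiplied by 0.84 to 1.74 through the analyte, passing through 1.00 where the two reference values coincide. The treatment comparison is unaffected, and this is a secondary pharmacodynamic analysis with no bearing on the primary endpoint.

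**What to change.** In Section 10.1.5, replace the reference sentence with one modelled on the FeNO and eosinophil rule: the LS means are taken at the mean of log baseline free sST2 in the free models and at the mean of log baseline total sST2 in the total models. It would also help to state, in the sST2 results presentation, whether per-arm percentage changes from the model are shown in Tables 6.2, 6.4, 6.6 and 6.8. The cost is one or two sentences, with no change to data, models or sample size.
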